Endpoint	The primary outcome will be the percentage of swallows with aspiration and/or penetration for cold milk compared with room temp milk (a total of 15 swallows will be assessed by VFSS and FEES). Based on our preliminary results, we expect to find a significant decrease in penetration and aspiration during the initial cold swallows (5 swallows). We expect this improvement to be sustained on the subsequent cold swallows (10 swallows) following the 15-minute cold liquid feeding. A decrease of 30% in penetration and/or aspiration with cold milk will be considered significant. Similarly, a 30% improvement of feeding coordination as assessed by nFant device will be considered significant.
	2. Evaluate the safety of feeding cold milk in preterm infants. We will evaluate whether cold milk will cause hypothermia (assessed by measuring Axillary temperatures), change in vital signs (respiratory rate, heart rate, and oxygen saturation) as well as change in mesenteric blood flow indices (assessed by abdominal ultrasound) These changes with cold milk feeding will be expressed as % change compared to base line (room temp milk).
Study Duration	2 years
Participant Duration	The subjects will participate in the study for approximately 48 hours during their NICU hospital stay
Population	Preterm Infants less than 34 weeks gestation admitted to NYU- Langone Long Island Hospital NICU. (n=42)
Study Sites	NYU- Langone Long Island Hospital
Number of participants	42

1. Introduction, Background Information and Scientific Rationale

Approximately half a million preterm infants are born every year in the USA.^{1,2} It is estimated that 30-70% of very low birth weight (VLBW) preterm infants will be diagnosed with swallowing dysfunction (dysphagia), with an inverse relationship between the severity of dysphagia and gestational age (GA).³⁻⁶ Although the pathophysiology of dysphagia is multifactorial,^{4,7-9} the discoordination between swallowing and breathing is the most prevalent cause of dysphagia in preterm infants,¹⁰ which often leads to airway compromise in the form of laryngeal penetration and/or tracheal aspiration into the lungs.^{7,11} Chronic airway compromise results in a persistent inflammatory state, with disease progression to chronic lung injury and *bronchopulmonary dysplasia (BPD)* that can be devastating for already fragile and developmentally immature lungs in preterm infants.^{4,7}

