For the study purpose, the FEES will be used to assess swallowing coordination with cold milk for a total of 15 swallows only.

Risks associated with FEES- FEES is a routine procedure done in the NICU and is ordered by the medical team. It is also possible that FEES will cause epistaxis, or respiratory distress during the FEES. Although it is unlikely given the previous reports in using it in preterm babies, as well as in adults and pediatrics. The diameter of the FEES scope is similar in size to the nasal gastric tube that most preterm infants have already, which is commonly well tolerated in preterm infants, even during oral feedings. Several studies demonstrated its safety in children. However the procedures will only be conducted in the presence of an attending Neonatologist to ensure airway safety in case of any adverse events. The FEES will be ordered by the medical team as clinically indicated (the clinician can do the FEES for the entire feeding or portion of the feeding).

Development of cold stress in response to cold liquids- It is possible that infants feeding cold liquids will develop cold stress. Several studies have assessed the effects of cold feeds in healthy term and healthy preterm infants but not in the context of dysphagia. These studies revealed no significant adverse effects including no difference in sleep pattern, vocalizations, motility, intake, feeding behavior, weight gain, temperature or regurgitation.²⁶ Blumenthal and colleagues²⁷ reported that cold feeds were well tolerated and produced no obvious clinical effects. Other studies found no significant differences in gastric residuals in preterm infants (28-30 weeks gestation age) fed cold (0-4°C) versus room temperature (25°C) milk,²⁸ as well as no effect regarding gastric emptying time.^{27,29} Based on the current literature in preterm infants, the 15-minute exposure to cold liquid is expected to result in little risk.³⁰

Cold Stress Prevention - As part of our study design, we are employing frequent axillary and gastric content temperature checks to ensure participant safety. Furthermore, infants' vital signs (blood pressure, respiratory rate, heart rate, and oxygen saturation), and evidence of any respiratory compromise, will be monitored and recorded.

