Radiation Exposure - For this study, we aim to visualize 15 swallows, which will take approximately 18 seconds. Compared to the typical range of radiation time of 90-180 seconds in routine VFSS. The radiation exposure related to this research equals 10-20% of what an infant would be exposed to during a typical routine VFSS.

Radiation Exposure Prevention – Our study design will include various radiation sparing techniques: 1) Commination, which restricts the x-rays to a smaller area on the subject; 2) Pulsed fluoroscopy, which takes 30 frames/second, instead of the continuous fluoroscopy of 60 frames/second; 3) The radiologist will utilize intermittent fluoroscopy to turn the radiation on only at the time of swallowing; 4) A lead shield will be placed on the subjects' lap to protect reproductive organs from radiation scatter.

Known Potential Benefits

The subjects may or may not personally benefit from being in this study. The results of this research (the safety and effectiveness of cold milk for each subject) will be disclosed to the medical team for further consideration. If the

results confirm safety and efficacy for that infant, the medical team can consider using cold milk to treat the infant's dysphagia which can be a significant benefit to the subject.

3. Objectives

The first objective is to identify preliminary evidence for the efficacy of feeding full oral cold milk for dysphagia management in preterm infants. We hypothesize that oral feeding of cold milk in preterm infants with dysphagia will improve suck/swallow/breathe coordination and decrease penetration/aspiration to the airway. Our second objective is to confirm the safety of this practice. We hypothesize that cold milk intervention will have no adverse effects on intestinal blood flow as assessed by Doppler Ultrasound. These objectives are significant because there is a critical need to identify effective and safe evidence-based treatment options for dysphagia management in preterm infants.

4. Study Design

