- The axillary temperature will be measured immediately prior to and after each feeding condition. It will also be measured at 10, and 30 minutes after the CS feed, at the same time the gastric content temperatures are taken. Infants' vital signs will be recorded (blood pressure, respiratory rate, heart rate, and oxygen saturation), as well as evidence of bronchospasm, lethargy, respiratory distress, apnea, tachypnea, cyanosis, bradycardia, or tachycardia.
- Doppler ultrasound (Sonosite Edge Ultrasound system, Sonosite, Inc, WA) will be used to measure
 intestinal blood flow indices including the superior mesenteric artery flow (SMA), peak systolic velocity,
 SMA mean velocity, SMA end-diastolic velocity, resistive index, pulsatility index, portal vein volumetric
 blood flow, as well as heart rate and mean arterial blood pressure. Intestinal blood flow monitoring via
 Doppler ultrasound will be performed 6 times for each participant, performed one hour before and at 30 and
 60 minutes after both bedside feeding conditions (RTS and CS). Measurements will be taken at the bedside
 in the supine position.
- Step 2 (done 24-48 hours after step 1):
 - Infants will be transported to the radiology suite and undergo VFSS and or FEES, as ordered by the treating
 medical team (Figure1: the blue boxes indicate procedures done for research purpose only. None of the
 research procedures are experimental and are approved tests for neonates including VFSS, FEES, nfant
 test and abdominal ultrasound).
 - Routine procedure for VFSS or FEES will be followed as ordered by the medical team. This procedure is part of the routine clinical care and not considered part of the research study.
 - If no dysfunction is noted, the procedure will end, and the child will no longer be eligible for further participation in this research study. If dysfunction (penetration/aspiration) either on the VFSS or FEES study is noted, the child will be eligible to participate in the next phase of the study.
 - Immediately following the initial VFSS-FEES assessment, the infants will remain in the same seated position with the FEES scope in place. While keeping all variables from the standard VFSS-FEES the same, the infant will be fed cold barium (4-9°C) using the same nipple. A total of 5 swallows will be visualized using VFSS and FEES, labeled "Cold Swallows-1 (CS1)." These 5 swallows assessment are done for the research purpose only.

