 - If the dysphagia didn't improve, the study would end, and the child will no longer be eligible for participation further in this research study.
 - If the dysphagia improves with cold liquid, VFSS will then be turned off and the infants will then be fed their regular feeds (formula or expressed breast milk as indicated by the medical team) chilled to an approximate temperature of 4-9°C for a total of 15 minutes, or until the infant shows signs of feeding completion. The cold feeding will be replaced every 5 minutes to make sure that the temperature is maintained at 4-9°C to minimize habituation effect.³⁰
 - After the 15 minute period, the infant will be re-assessed by VFSS-FEES using cold barium from the same bottle (10 swallows, labeled "Cold Swallows-2" [CS2]). This design evaluates whether a full feeding of cold liquid will result in decreased penetration or aspiration compared to RTS condition. These 10 swallows assessment are done for the research purpose only).
 - The axillary temperature will be monitored every 10 minutes. Infants' vital signs (blood pressure, respiratory rate, heart rate, and oxygen saturation), as well as evidence of any respiratory compromise, will be recorded. A neonatologist will be next to the baby at all times. The baby will return to the NICU after the study accompanied by the NICU team, including the neonatologist.

Study #: i20-00876

Version Date: 6/13/2022

Depending on the scheduling of the VFSS/FEES testing by the infant's medical team, the research team might need to do Step 2 before Step 1, as described above. There will be at least 24 hours period between the two steps.

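### The 15-swallow primary outcome is complete only in infants who improved on the first 5 cold swallows, and the plan names no analysis set and no rule for infants stopped there

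*Combined protocol and SAP*

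**What the plan says.** The Endpoint row of the synopsis gives the primary outcome as a percentage of swallows, cold against room temperature, and adds that "a total of 15 swallows will be assessed by VFSS and FEES". It expects a fall on the first 5 cold swallows and continues: "We expect this improvement to be sustained on the subsequent cold swallows (10 swallows) following the 15-minute cold liquid feeding". It also sets a benchmark: "A decrease of 30% in penetration and/or aspiration with cold milk will be considered significant". Whether the 30% is in percentage points or relative is not stated.

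Section 4 (Study Design, Step 2) builds the 15 from CS1 (5 swallows) and CS2 (10 swallows). Entry depends on the routine study: "If dysfunction (penetration/aspiration) either on the VFSS or FEES study is noted, the child will be eligible". Of that routine study, which supplies the RTS baseline, it says: "This procedure is part of the routine clinical care and not considered part of the research study". If dysphagia does not improve on CS1, "the study would end, and the child will no longer be eligible for participation further in this research study". Only improvers receive the cold feed and CS2. The section then describes the design as evaluating a full cold feeding against RTS, with no mention of that condition.

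Statistical Considerations compares RTS with CS by a Wilcoxon signed-rank test. It does not say whether CS means CS1, CS2 or both, and it names no analysis set and no rule for infants stopped after CS1. There and in section 6, the sample size counts test-positive infants; the only loss allowed for is a negative VFSS/FEES. Neither the rule for improvement nor the number of RTS swallows scored is given.

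**The concern.** Two thirds of the primary outcome is collected only in infants who did well on the other third. If the 15-swallow percentage is tested in infants who have all 15, CS1 is both the condition for continuing and part of the result. Infants whose RTS rate was high by chance also pass more easily, so regression to the mean adds to the apparent benefit, and it affects CS2 too.

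As written, this analysis, one keeping every test-positive infant, and one using CS1 alone are all compatible with the text, and they behave very differently when cold does nothing. The choice is left open until the data are seen. Section 4 also says that, if efficacy and safety are shown, clinicians could use cold milk without repeating these measures in each child, so a spurious positive result would carry into practice.

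**Working it through.** **The plan's own power.** Inputs from Statistical Considerations: mean change 30, SD 25, correlation 0.20, two-sided alpha 0.05, N = 25. The SD of a paired difference is 25 × √(2 × (1 − 0.20)) = 31.6. Simulating the signed-rank test gives 99.4% power, which agrees with the stated figure of more than 95%. This calculation gives every infant a full paired outcome.

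**Number of infants.** 42 × 0.60 = 25.2, but the plan states 30 positives. Both 25 and 30 are used below.

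**Selection with no cold effect, normal model.** Let D1 = RTS − CS1, D2 = RTS − CS2 and pooled D = (5·D1 + 10·D2)/15 = (D1 + 2·D2)/3. All SDs are 25 and all correlations 0.20 (the CS1–CS2 correlation is an assumption). Then Var(D1) = 1000, Cov(D1, D2) = 625 − 125 − 125 + 125 = 500, and E[D2 | D1] = 0.5·D1. An infant continues if D1 > c, and E[D1 | D1 > c] = 31.6 × φ(c/31.6) / (1 − Φ(c/31.6)).

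- Any fall (c = 0): D1 = 31.6 × 0.3989/0.5 = 25.2; D2 = 12.6; pooled (25.2 + 2 × 12.6)/3 = 16.8 points. Completers: 12.5 of 25.
- 30-point fall (c = 30): D1 = 31.6 × 0.2544/0.1714 = 46.9; D2 = 23.5; pooled 31.3 points. Completers: 25 × 0.1714 = 4.3.

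All of these falls are spurious.

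**Share of null trials favouring cold** (exact two-sided 5% signed-rank test, nominal 2.5%, 25 infants, 10,000 runs):

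- Any fall: pooled in completers 64%; CS2 alone in improvers 26%; CS1 versus RTS in all positives 2.4%.
- 30-point fall: pooled 20%; CS2 alone 9%. In about 76% of trials fewer than 6 infants complete. With 5 non-zero differences the smallest p is 2/2⁵ = 0.0625, so the test cannot reject. The lower rate reflects few infants, not absence of bias.
- With 30 infants, pooled: 74% and 34.5%.

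**Swallow-level model.** Assumptions not in the documents: five beta distributions for the infant event rate, and the number of RTS swallows scored; entry requires at least one RTS event. Section 2 puts 15 swallows at about 18 seconds and a routine VFSS at 90–180 seconds. At that pace 15/18 × 90 = 75 and 15/18 × 180 = 150 swallows, an upper guide. Null trials favouring cold, 25 infants:

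| RTS swallows | 5 | 10 | 20 | 75–150 |
|---|---|---|---|---|
| Any fall, pooled in completers | 62–96% | 51–81% | 43–62% | 32–43% |
| Any fall, CS2 alone in improvers | 21–64% | 8–25% | 5–12% | 2–6% |
| 30% relative fall, pooled | 13–90% | 11–72% | 7–53% | 7–40% |
| 30-point fall, pooled | 3–20% | 4–15% | 0.5–3% | 0–0.3% |
| Spurious fall, 30-point rule (points) | 29–32 | 20–22 | 18–19 | 13–15 |
| CS1 versus RTS, all positives | 3–19% | 2–8% | 1–5% | 1–5% |

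**Keeping every test-positive infant** (15 swallows for improvers, CS1 for stopped infants). Null trials favour cold in 0–6% with an any-fall rule. With a 30-point rule they do so in 2–14% with 5 RTS swallows and 1–5% with 10 or more. In the normal model the measure shifts against cold by (2/3) × 0.5 × 31.6 × φ, with φ taken at the cut-off standardised by the true effect. With no effect and an any-fall rule the shift is 10.53 × 0.3989 = 4.2 points. With a true 30-point effect the mean is 30 − 10.53 × 0.2544 = 27.3 (any fall) or 30 − 4.2 = 25.8 (30-point rule). Power with 25 infants is 98–99%.

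**Completers under a true 30-point effect** overstate it: 36.4 pooled and 34.7 for CS2 (any fall), or 46.8 and 42.6 (30-point rule).

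**The case against.** A reader might infer that the plan commits to a completers-only test, and so that this trial's false-positive rate is 64% or even 96%. The documents do not support that. No section restricts the analysis to completers, and the sample size is built on all test-positive infants. The outcome is a percentage, which a stopped infant also has from CS1. Section 2 uses 15 as the number of swallows viewed: "the FEES will be used to assess swallowing coordination with cold milk for a total of 15 swallows only", and "we aim to visualize 15 swallows, which will take approximately 18 seconds". All of this stands. What is established is an unstated analysis set, with one natural reading of the endpoint that is invalid.

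It is also fair that the largest figures need few RTS swallows, a count the plan does not give. If the routine recording yields many, CS2 alone is near nominal. Pooling in completers stays inflated under an any-fall or relative-fall rule. Under a 30-point rule it almost never rejects but still shows a spurious fall.

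A second tempting inference is that CS1 versus RTS should become the sole primary test. Section 1 says the 5-swallow effect has already been shown and that a full-duration feed is what remains to be validated. A CS1-only primary would repeat the known contrast and drop that objective. Nor is it cleaner: in the settings run, it favoured cold in more null trials than the analysis that keeps stopped infants.

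Persistence of benefit among early improvers is a legitimate question, provided it is labelled as such.

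**Conclusion.** The concern holds as a gap in the definition of the primary analysis. The plan does not say which cold swallows, which infants, or what value for stopped infants. If completers alone are tested on the pooled 15 swallows, null trials favour cold in about 64% (any fall) or 20% (30-point fall) with 25 infants, and in about 74% or 35% with 30, against 2.5%. These figures use the plan's SD and correlation and an assumed CS1–CS2 correlation of 0.20. At swallow level with an any-fall rule the range is about 30–96%, depending on the assumed RTS count and event rates. With a 30-point rule and many RTS swallows rejection is near zero, but a spurious fall of about 13–15 points remains.

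Section 4's statement that the design evaluates a full cold feeding against RTS therefore holds only for early improvers, unless stopped infants are kept in the analysis.

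**What to change.** In the Endpoint row and in Statistical Considerations:

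- Name all VFSS/FEES-positive infants who receive CS1 as the primary analysis set, and do not test the pooled 15-swallow percentage in completers only.
- Define the cold percentage as the 15-swallow value for improvers and the CS1 value for infants stopped after CS1. This keeps the full-feed question.
- Report CS1 versus RTS in the same set alongside it as the initial-swallow result (about 99% power at the plan's effect).
- Report CS2 in improvers, with the number of infants, as conditional on early response, and add that condition to section 4's sentence on a full cold feeding.
- State, before data are seen, the rule used for improvement and the number of RTS swallows to be scored from the routine recording.

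The cost is wording and analysis: no extra infants, cold swallows or radiation, and no change to the clinical stopping rule. The RTS count is limited by what the routine recording holds.

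Downsides: the all-infant measure mixes the CS1 and CS2 periods and is conservative under an any-fall rule. With an error-free RTS rate and no cold effect it averaged about 5 points against cold, and its two-sided test rejected in 32–39% of trials. A result against cold should therefore be read beside CS1 versus RTS. Both all-infant analyses keep some bias from requiring a positive RTS study when few RTS swallows are scored. With 5 RTS swallows and low event rates, favourable null rejections reach about 14% for the all-infant measure and 19% for CS1 versus RTS.

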This will be a prospective study, with each infant serving as their own control. All study subjects will meet the inclusion/exclusion criteria listed in Section 5 of this proposal and informed consent will be obtained. The subject will be considered for the study if the medical team diagnosed the infant with clinical dysphagia and decided to obtain Video Fluoroscopic Swallow Study (VFSS), or Fiberoptic Endoscopic Evaluation of Swallowing [FEES) or both to help manage the dysphagia (such as delay oral feeding till the child is more mature or use feeds thickeners). The VFSS and FEES are not a requirement for step 1 however abnormal VFSS and FEES are requirement for step 2.

The following study procedures will be done before the routine VFSS/FEES testing ordered by the medical team:

Study Protocol Timeline

• Step 1 (bedside procedures):

- We will evaluate the infant's sucking, swallowing, and breathing patterns using a non-invasive FDA approved equipment (nFant® Feeding Solution). This device is in clinical use for several years and routinely used in several NICUs. The nFant has a wireless sensor within the nipple to assess sucking and swallowing coordination during feeding. This machine is not routinely used in NYU- Langone Long Island Hospital NICU because of costs but will be available only for infants enrolled in this research study. The nfant assessments will be performed by the research team under two separate feeding conditions, standard room temperature (RTS) and cold temperature (CS, at 4-9°C) of milk/formula for an entire feeding (15-20 minutes). The two feedings will be done on the same day but may not necessarily be two consecutive feedings (depending on the baby's eagerness to feed orally). The order of each condition will be randomized to control for fatigue. Inter- and intra-rater reliability measures will be calculated. The nfant assessments will include the following measurements:
 - peak amplitude the displacement of the nipple during compression phase normalized from a calibrated 0% to 100%;
 - duration how long or drawn out sucking events are from onset to end in seconds;

- frequency the rate at which consecutive suck events are occurring in Hertz;
- > suck bursts number of sucks per burst, duration and number of bursts, and active time spent sucking;
- > suck smoothness the number of velocity changes in a nipple amplitude trace during a suck.

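### The post-feed cold swallows (CS2) have no room-temperature comparator at the same point in a feed, so CS2 cannot show the effect of a full cold feed against room temperature

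*Combined protocol and SAP*

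**What the plan says.** The Synopsis (Endpoint) defines the outcome: "The primary outcome will be the percentage of swallows with aspiration and/or penetration for cold milk compared with room temp milk". It adds that "a total of 15 swallows will be assessed by VFSS and FEES". Those 15 are the 5 swallows of CS1 plus the 10 of CS2, and all are cold.

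Section 4, Step 2, gives the sequence:

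1. The clinical study: "Routine procedure for VFSS or FEES will be followed as ordered by the medical team". Only infants with penetration or aspiration on it continue. The number of swallows in this block is not stated. That it is at room temperature is implied by the RTS label and the endpoint wording, not stated in Step 2.
2. CS1, straight afterwards: "the infant will be fed cold barium (4-9°C) using the same nipple", for 5 imaged swallows.
3. A gate: "If the dysphagia didn't improve, the study would end, and the child will no longer be eligible for participation further in this research study".
4. A chilled feed of the infant's usual milk for 15 minutes, or less if the infant finishes sooner, with VFSS off.
5. CS2: 10 imaged cold swallows.

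The protocol then says of this sequence: "This design evaluates whether a full feeding of cold liquid will result in decreased penetration or aspiration compared to RTS condition". The Synopsis predicts the result: "We expect this improvement to be sustained on the subsequent cold swallows (10 swallows) following the 15-minute cold liquid feeding".

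For the two nFant feeds in Step 1, by contrast, "The order of each condition will be randomized to control for fatigue". The Statistical Considerations plan a paired Wilcoxon signed-rank test of RTS against CS, with no term for order or time. They do not say whether CS means CS1, CS2 or both.

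**The concern.** An infant at CS2 differs from the same infant at RTS in two ways. The liquid is cold, and the infant has fed for up to 15 minutes. Fatigue late in a feed could raise the event rate. Satiety, slower sucking or adaptation to the setting could lower it. With no room-temperature observation at the same point, the two differences cannot be separated.

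This touches what the trial is meant to add. The Introduction says the group has already published the short, 5-swallow effect and that the full-duration feed still needs validation. CS2 is the only planned research imaging after a full feed, so the block that carries the new question is the one mixed with time. If CS1 and CS2 are pooled, the same problem enters the primary comparison.

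**Working it through.** **1. Share of cold swallows after the feed.** For an infant who completes Step 2: 10/15 = 66.7%. For an infant stopped at the CS1 gate: 0 of 5. Planned room-temperature swallows after the feed: 0.

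**2. Features that might control for time.**
- Order is randomised in Step 1 only. The nFant measures there describe sucking, not penetration or aspiration.
- Holding conditions constant is stated for CS1, not for the swallows after the feed.
- Replacing the milk every 5 minutes keeps it cold. It does nothing about fatigue or satiety.
- Step 2 may be done before Step 1, but the order within Step 2 does not change.

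None supplies a time-matched comparator.

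**3. The plan's own power figure.** Inputs from Section 6: mean change 30, SD 25, correlation 0.20, two-sided alpha 0.05, N = 25.
- SD of the difference = 25 × √(2 × (1 − 0.20)) = 31.6; standardised change = 30/31.6 = 0.95.
- Simulated Wilcoxon power (10,000 samples) is 99.2%; the paired t-test gives 99.5%. The stated figure of more than 95% is met.
- The calculation has no drift between the RTS and cold measurements. With no drift and no effect, the simulated false-positive rate is 4.9%.

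**4. Bias from a time effect (illustrative).** The documents give no drift. Let d be an assumed shift in event rate, in percentage points, from before to after the feed, and let p be the assumed fraction of infants who pass the CS1 gate.
- CS2 versus RTS: bias = d.
- Pooled 15 swallows, infant who completes: bias = (10/15) × d.
- Pooled, mean over all infants: bias = p × (10/15) × d.

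| Assumed d | CS2 alone | Pooled, completers | Pooled, mean at p = 0.5 |
|---|---|---|---|
| 5 | 5 | 3.3 | 1.7 |
| 10 | 10 | 6.7 | 3.3 |
| 15 | 15 | 10.0 | 5.0 |

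**5. Effect on the test (illustrative).** Same planning inputs, with all 25 infants assumed to reach CS2.

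| Assumed d | Significant, no temperature effect, drift favours later swallows: CS2 / pooled | Power, true 30-point effect, drift against cold: CS2 / pooled |
|---|---|---|
| 5 | 11.5% / 7.4% | 95.8% / 97.5% |
| 10 | 32.1% / 16.1% | 83.9% / 93.2% |
| 15 | 59.8% / 31.2% | 60.2% / 84.1% |

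These rates show how sensitive the contrast is. They do not predict what will happen in this trial.

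**The case against.** **The order is largely forced.** The routine study is clinical care and decides eligibility for the rest of Step 2, so it has to come first. This stands. The fault is the inference drawn from the sequence, not a failure to randomise something that could easily have been randomised.

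**Fatigue is the only time effect the protocol names, and it works against cold.** On that account a favourable CS2 result would be conservative. This stands in part. It means a reader should not infer that CS2 is uninformative or that the bias must flatter cold milk. But satiety and adaptation could act the other way, and the documents give no basis for the net direction.

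**The bias sizes are assumptions.** This stands. A reader might infer that the bias reaches a third of the planned effect, since 10/30 = 1/3. That comes only from choosing d = 15, pooling the two blocks and having every infant pass the gate. The documents give no drift, and the analysis text does not specify pooling.

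**CS1 versus RTS also has a fixed order.** This stands. The gap is short because CS1 follows immediately, but order is not controlled. Selection on an abnormal routine study means that some fall could occur without any temperature effect.

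**Some routine imaging may span a feed.** The FEES risk text lets the clinician run FEES for all or part of a feeding. This may happen in some infants, but it is not a planned comparator.

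**The aims are preliminary.** The Synopsis and Section 3 say so, and looking at persistence after a feed is a reasonable preliminary aim. That supports describing CS2 as persistence. It does not support calling it a comparison of a full cold feed with RTS.

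A reader might also infer that room-temperature swallows should be added after the feed. The documents do not support that as a simple repair. It would add a research exposure to the condition in which these infants showed penetration or aspiration. The sensory effect of the cold feed might carry over into those swallows, and within the same total it would leave fewer cold ones. Whether any such comparison is acceptable is for the clinical team.

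**Conclusion.** The point holds as a limit on what CS2 can show. The sequence, the absence of a time-matched room-temperature observation and the lack of any order or time term are all in the plan. The claim that Step 2 evaluates a full cold feed against RTS is therefore unsupported.

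The possible bias is d for CS2 alone and (2/3)d for a pooled percentage in infants who complete Step 2. It is smaller on average when some stop at CS1. Neither the size nor the sign of d can be taken from the documents. The conclusion assumes that the routine study is at room temperature, as the RTS label implies.

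It does not follow that the whole primary comparison is invalid. CS1 against the swallows just before it is little affected by time in the feed, though its fixed order and the selection of infants remain. Nor does the stated power fail: it reproduces under its own no-drift inputs.

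**What to change.** 1. In the Statistical Considerations, define the primary temperature contrast as CS1 versus the immediately preceding RTS swallows, and state that CS1 and CS2 are not pooled. Record as limitations that this order is also fixed and that infants are selected on an abnormal routine study.
2. Report CS2 separately and descriptively, with a confidence interval, as persistence after a cold feed among infants who improved at CS1. Give the number who reached it.
3. Reword the Step 2 sentence to say that CS2 describes whether the CS1 result persists after a cold feed in those infants, and that it does not compare a full cold feed with a room-temperature feed. Align the Endpoint expectation in the Synopsis.
4. Label any figure for time-related bias as illustrative.

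**Cost.** No added swallows, imaging or infants; only wording and analysis labels change. The trial makes a narrower claim about full feeds. The primary contrast rests on 5 cold swallows per infant, so each cold percentage moves in steps of 100/5 = 20 points rather than 100/15 = 6.7. The documents do not tie the planning SD of 25 to a number of swallows, so the team should confirm that it applies to 5.
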